17.1.4. SENSITIVITY ANALYSIS OF PRIMARY EFFICACY VARIABLE(S)

There will be no sensitivity analysis for this exploratory study.

17.2. SECONDARY EFFICACY

17.2.1. SECONDARY EFFICACY VARIABLES & DERIVATIONS

17.2.1.1. Change in mJDA Severity Index Total Skin Lesions Score At All Study Visits

The mJDA severity index is used to determine the primary endpoint, but itself is not a primary efficacy

variable. Individual components of the mJDA severity index are used for secondary efficacy analysis. Table D shows the mJDA questionnaire.

Table D. Modified Japanese Dermatological Association (mJDA) Worksheet

	Score	Score						
	0	1	2	3				
Assessment of skin lesions	Assessment of skin lesions							
Area of erythema with pustules	0%	>0%, <10%	≥10%, <50%	≥50%				
Total area of erythema	0%	>0%, <25%	≥25%, <75%	≥75%				
Area of edema	0%	>0%, <10%	≥10%, <50%	≥50%				
Assessment of systemic manife	stations and lal	ooratory findings						
Fever (°C)	<37.0	≥37.0, <38.5	≥38.5	n/a				
WBC count (/µL)	<10 000	≥10 000, <15 000	≥15 000	n/a				
CRP (mg/dL)	< 0.3	≥0.3, <7.0	≥7.0	n/a				
Serum albumin (g/dL)	≥3.8	<3.8,≥3.0	<3.0	n/a				

The scores (0 to 3 for skin lesions, and 0 to 2 for systemic manifestations and laboratory findings) as well as the actual values of all seven mJDA assessments will be captured in the eCRF.

The total score will be calculated as follows and is the sum of these 7 scores:

Severity Index Total Score = Sum of scores for: Area of erythema with pustules, Total area of erythema, Area of edema, Fever, WBC count, CRP, Serum albumin The severity index total score will be categorized as follows in the listings: 1-6 = Mild, 7-10 =

Moderate, and 11-17 = Severe.

Severity Index Total score at Visit X = Sum of all 7 mJDA scores at Visit X.

Severity Index Total score at Baseline = Sum of all 7 mJDA Baseline scores.

Change at Visit X = Severity Index Total score at Visit X – Severity Index Total score at Baseline

Descriptive statistics (including n, mean, SD, median, minimum, and maximum) will be presented for each measurement time for all study visits. Each subject's change in mJDA Severity Index Total score will be plotted over all study visits.

The change from Baseline in the mJDA severity index total skin lesions score is the sum of erythema, erythema with pustules, and edema scores. The change in score for each visit can range from -9 to 9 and will be calculated as follows:

Total Skin Lesions Score at Visit X = Sum of the scores at Visit X for: Area of erythema with pustules, Total area of erythema, Area of edema.

Total Skin Lesions Score at Baseline = Sum of the scores at Baseline for: Area of erythema with pustules, Total area of erythema, Area of edema.

Change at Visit X = Total Skin Lesions Score at Visit X – Total Skin Lesions Score at Baseline

Descriptive statistics (including n, mean, SD, median, minimum, and maximum) will be presented for each measurement time for all study visits. Each subject's change in mJDA total skin lesion score will be plotted over all study visits.

17.2.1.2. Change in Affected Area of Erythema With Pustules, Erythema, and Edema at All Study Visits

The change from Baseline in each of the measurements: percent area of erythema, percent area of erythema

with pustules, and percent area of edema at all study visits will be calculated.

The change for each visit for each area percentage will be calculated as follows:

Area % at Visit X = The percentage from the mJDA assessment.

Area % at Baseline = Total percentage from the mJDA assessment at Baseline

Change at Visit X = Area % at Visit X – Total area % at Baseline

Descriptive statistics (including n, mean, SD, median, minimum, and maximum) will be presented at each measurement time for all study visits. An overlay plot of each subject's value over all study visits will be presented for each component score.

17.2.1.3. Change in Total and Individual Scores in Systemic Manifestations and Laboratory Findings as Measured by mJDA Severity Index at All Study Visits

The change from Baseline of the total and the four individual scores in systemic manifestations and laboratory findings, as measured by the mJDA at all study visits, will be summarized in the same manner as the change in mJDA severity index total skin lesions score.

Change in the total score for each visit can range from -8 to 8 and will be calculated with the following derivations:

Total score at Visit X = Sum of scores at Visit X for: Fever, WBC count, CRP, Serum albumin Total score at Baseline = Sum of scores at Baseline for: Fever, WBC count, CRP, Serum albumin Change at Visit X = Total score at Visit X – Total score at Baseline

Change in the four individual scores for each visit can range from -2 to 2 and will be calculated as follows:

Fever Score Change at Visit X = Fever Score at Visit X – Fever Score at Baseline

The same formula will be applied to calculate the **Score Change at Visit X** for the **WBC Count, CRP** and **Serum albumin**.

Descriptive statistics (including n, mean, SD, median, minimum, and maximum) will be presented at each measurement time at all study visits for each numeric systemic manifestation and laboratory finding. An overlay plot of each subject's value over study visits will be presented for each measurement at all study visits.

17.2.1.4. Proportion of Subjects Achieving A GPPPGA Score of 0 or 1 at Post-Baseline Study Visits

The GPPPGA is a physician-based assessment of GPP, performed at every visit (except phone calls). The severity and impact of the subject's erythema, pustules, and scaling/crusting of pustular psoriasis lesions is scored on a 5-point scale as shown below in **Table E. Scoring of** GPPPGA.

Score	Wording	Detailed description
0	Clear	Normal skin or post-inflammatory hyperpigmentation, no visible pustules, no scaling or crusting
1	Almost clear	Faint, diffuse pink or slight red erythema, low density occasional small discrete pustules (non-coalescent), superficial focal scaling or crusting restricted to periphery of lesions
2	Mild	Light red erythema, moderate density grouped discrete small pustules (non- coalescent), predominantly fine scaling or crusting
3	Moderate	Bright red erythema, high density pustules with some coalescence, moderate scaling or crusting covering most or all lesions
4	Severe	Deep fiery red erythema, very high-density pustules with pustular lakes, severe scaling or crusting covering most or all lesions

Table E. Scoring of GPPPGA

Statistical Analysis Plan

The GPPPGA will be summarized at each post-baseline visit for the proportion of subjects achieving a score of 0 or 1 as opposed to a 2, 3 or 4. The proportion of subjects having a GPPPGA score of 0 or 1 will be derived using all subjects randomized and enrolled as the denominator for this calculation.

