## Appendix 13 Summary of Changes

### **Protocol ANB019-002: Amendment 1, 15 January 2018**

#### **Replaces: Original Protocol, 12 December 2017**

Section 1.1 Synopsis, Section 4.1 Overall Design and Table 1 Schedule of Activities (footnote)

- Description of Change: Added text to indicate that a minimum 3 hour observation period is required after the first and second subcutaneous injections and deleted from the following text ‘no such limit for study center observation after SC administration’.
- Purpose of Change: Medicines and Healthcare Products Regulatory Agency (MHRA) request.

Section 5.1 Inclusion Criteria and Appendix 6 Contraceptive Guidance and Collection of Pregnancy Information:

- Description of Change: Text revised to specify that in addition to prohibition on sperm donation for the specified duration, ova donation for assisted reproduction is also prohibited. The duration for males was revised to 220 days (from 6 months).
- Purpose of Change: MHRA request.

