### **Protocol ANB019-002: Amendment 3, 20 March 2019 Replaces: Amendment 2, 27 July 2018**

#### Title Page:

- Description of the change: Title page updated to reflect ‘Amendment 3.’
- Purpose of the change: Administrative change.

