### Synopsis and Section 3:

- Description of the change: Additional wording added to the secondary endpoints for PK analysis; moved immunogenicity objective (to assess ADA) from exploratory to secondary endpoint; retitled *tertiary/exploratory* endpoints section to *exploratory* endpoints.
- Purpose of the change: To capture an additional endpoint and to better clarify the PK and pharmacogenomic testing; to place greater emphasis on immunogenicity testing.
- Description of the change: Added an additional secondary endpoint to assess the proportion of subjects achieving a score of 0 or 1 on the Generalized Pustular Psoriasis Physician's Global Assessment scale.
- Purpose of the change: To further characterize efficacy assessments for GPP.

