#### 8.1.4 Generalized Pustular Psoriasis Physician’s Global Assessment Scale

- Description of the change: New section added to describe the GPPPGA scale.
- Purpose of the change: This assessment scale was added as a secondary endpoint to assess the impact of GPP at each study visit. Appendix 12 was also added to include the scale.

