#### Appendix 11 Generalized Pustular Psoriasis Physician's Global Assessment

- Description of the change: New appendix was added.

- Purpose of the change: To support the added secondary endpoint of the GPPPGA assessment at each study visit.

In addition, minor spelling, grammar, abbreviations, editing, and formatting corrections have been made throughout, as needed.

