17.2.2. MISSING DATA METHODS FOR SECONDARY EFFICACY VARIABLE

If GPPPGA score is missing for a subject, for any reason, the score will not be imputed. Missing values for DLQI will be replaced using Last Observation Carried Forward (LOCF) for summarization of the results. All other missing values for secondary efficacy assessments will remain missing and not be imputed for any summary calculations.

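### GPPPGA was added by Amendment 3, but the 0/1 proportion divides by all enrolled subjects at every visit, so any visit held before the scale was in use would count as not achieving 0/1

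*SAP*

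**What the plan says.** **Denominator.** SAP 17.2.1.4 states: "The proportion of subjects having a GPPPGA score of 0 or 1 will be derived using all subjects randomized and enrolled as the denominator". The same section describes GPPPGA as done at all visits other than phone contacts, and sets scores of 0 or 1 against scores of 2, 3 or 4. SAP 17.2.3 places all secondary efficacy analyses on the FAS. The FAS definition in SAP section 8 has no condition on protocol version or on whether the scale was in use.

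**Missing scores.** SAP 17.2.2 states: "If GPPPGA score is missing for a subject, for any reason, the score will not be imputed".

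**When the scale arrived.** Protocol Appendix 13 lists the protocol history from the "Original Protocol, 12 December 2017" onward. The relevant entry is "Amendment 3, 20 March 2019 Replaces: Amendment 2, 27 July 2018". Under it, the entry for section 8.1.4 reads "New section added to describe the GPPPGA scale" and gives the purpose: "This assessment scale was added as a secondary endpoint to assess the impact of GPP at each study visit". The entry for the synopsis and section 3 reads "Added an additional secondary endpoint to assess the proportion of subjects achieving a score of 0 or 1". The new Appendix 11 is explained as "To support the added secondary endpoint of the GPPPGA assessment at each study visit".

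**Version the SAP was written for.** SAP section 1 names Amendment 4, dated 30 August 2019. In that version GPPPGA is already scheduled at every clinic visit. The SAP makes no provision for visits held under earlier versions.

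**The concern.** The SAP treats two kinds of missing score alike. One is a score that was due but not obtained, through dropout, early termination at Week 4 or a missed rating. Keeping such subjects in the denominator is a reasonable conservative choice. The other is a score that was never due, because the scale was not yet in the protocol in force at the site. That gap says nothing about response: the subject may have attended the visit and been clear. With an all-enrolled denominator and no imputation, both kinds count as not achieving 0/1.

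GPPPGA 0/1 is the trial's clear or almost clear endpoint. If any subject had visits before the scale was in use, the reported percentage at those visits would depend partly on when the subject enrolled. Change from baseline in GPPPGA (SAP 17.2.1.5) would behave differently: a subject without a baseline score simply drops out of it. The two GPPPGA results could then describe different groups of subjects.

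**Working it through.** The plan gives no expected GPPPGA rate, power or alpha, and its sample size is not power-based. There is therefore no planned figure to reproduce, and the check is direct arithmetic.

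**Inputs**
- N = 10: planned enrolment of about 10 (SAP 5.2).
- Denominator: all enrolled (SAP 17.2.1.4). Missing score: not imputed (SAP 17.2.2).
- Earliest date the scale could be in use: 20 March 2019 (Appendix 13). Protocol Appendix 2 requires ethics approval and, where applicable, regulatory approval before an amendment is implemented, so the effective date at a site may be later.
- k = number of subjects for whom GPPPGA was not yet scheduled at a given visit. The documents do not give k. Assumed range for illustration: 0 to 3.
- x = number of subjects rated 0 or 1. Assumed to be about 80% of those rated, rounded to a whole number, with no other missing scores.

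**Step 1: effect on the proportion**

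SAP proportion = x/N. Proportion among those for whom the scale was scheduled = x/(N − k). Highest attainable SAP proportion = (N − k)/N. Intervals are exact (Clopper-Pearson) 95%.

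| k | x | x/10 as in the SAP | x/(10 − k) | Highest attainable under the SAP |
|---|---|---|---|---|
| 0 | 8 | 80.0% (44.4 to 97.5) | 80.0% (44.4 to 97.5) | 100% |
| 1 | 7 | 70.0% (34.8 to 93.3) | 77.8% (40.0 to 97.2) | 90% |
| 2 | 6 | 60.0% (26.2 to 87.8) | 75.0% (34.9 to 96.8) | 80% |
| 3 | 6 | 60.0% (26.2 to 87.8) | 85.7% (42.1 to 99.6) | 70% |

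The last column does not depend on the assumed response rate: each affected subject costs 1/10 = 10 points.

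**Step 2: which visits could be affected**

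A Day d visit falls before 20 March 2019 if Day 1 was before 20 March 2019 minus (d − 1) days.

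- Week 4 (Day 29): minus 28 days, so Day 1 before 20 February 2019.
- Week 16 (Day 113): minus 112 days, so Day 1 before 28 November 2018.
- Week 24 (Day 169): minus 168 days, so Day 1 before 3 October 2018.

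These are nominal days and take the amendment date as the effective date. Later implementation at a site moves each cut-off later by the same delay. The gap is therefore specific to a visit. Only a subject dosed before about 3 October 2018 would have had every visit before the amendment date. A subject dosed later, but before the scale was in use, would lack a baseline and early scores and could still be rated afterwards.

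**The case against.** The strongest objection is that the premise is undocumented. A protocol dated December 2017 does not show that anyone was dosed before Amendment 3, and the current protocol and SAP agree with each other on when GPPPGA is collected. This stands, and it makes the point conditional.

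There is also indirect evidence that few subjects, if any, are affected. Amendment 4 (30 August 2019) added the paragraph on interim timing, worded as a future event. One of its triggers is at least 2 subjects at 16 weeks after dosing. Anyone dosed before 20 March 2019 and still in the study would have reached Day 113 by about 9 July 2019 (19 March plus 112 days), so two such subjects would already have met that trigger. This is inference only: subjects terminated at Week 4 would not count, and a delay at a site could affect subjects dosed after 20 March. Still, it makes two or more early subjects less likely.

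Third, the study is exploratory with no hypothesis test, and the SAP offers some visibility. Each subject's GPPPGA is plotted over all visits (17.2.1.5), and Appendix 1 asks for denominators to be identified. That would help a careful reader notice a subject without scores. It would not correct the percentage in the table.

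A reader might infer that every subject treated under an earlier version has no GPPPGA at all, or that the reported proportion is known to be too low. The documents support neither: the gap is by visit, and the number of subjects affected may be zero.

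**Conclusion.** The rule as written gives the wrong result for any visit held before Amendment 3 took effect at the site: a scale not yet scheduled is counted as not achieving 0/1. This follows from the denominator and the no-imputation rule together; the SAP does not itself label such subjects failures.

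The size depends on k, which the documents do not give. At k = 0 there is no effect. At N = 10 the ceiling on the reported proportion at an affected visit is 90% for one subject and 80% for two. The percentages in the table also rest on the assumed response rate and on no other missing scores. The sponsor can settle k from dosing dates and the date Amendment 3 came into force at each site.

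The point concerns a descriptive secondary endpoint. It is worth correcting before database lock because the correction is cheap and the SAP otherwise has no rule for these visits.

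**What to change.** In SAP 17.2.1.4:

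- Define the denominator at each visit as enrolled subjects for whom GPPPGA was in the protocol in force at their site at that scheduled visit. Dropouts, subjects terminated early and missed ratings remain in it.
- Show that N and the number actually rated, by visit.
- Footnote the subjects and visits for which GPPPGA was not yet scheduled.
- Keep the all-enrolled proportion as a labelled sensitivity result.
- Delete the reference to randomization, which does not apply to a single-arm study.

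Do not make a baseline GPPPGA a condition for the 0/1 endpoint. A score of 0 or 1 is an absolute state at a visit, and such a condition would discard valid later scores. For SAP 17.2.1.5 it is enough to show n, because subjects without a baseline already drop out of the change.

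The cost is a definition, a footnote and one extra line in the table. The small downside is that the GPPPGA denominator may be below the FAS N and may differ between visits.

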17.2.1.5. GPPPGA Change from Baseline Scores at All Study Visits

The change from Baseline in GPPPGA will be summarized at each postbaseline visit. A separate overlay

plot will display each subject's GPPPGA score over all study visits and another for each subject's change from baseline scores over all study visits.

17.2.1.6. PASI Score Summary

PASI scores will be used to determine the treatment response in subjects with plaque psoriasis. The PASI total score includes 12 plaque characteristic (i.e. erythema, induration, scaling) scores and four percentages of BSA affected.

Table F Psoriasis Area Severity Index Score (PASI) shows the PASI worksheet. Details for these calculations appear in the PASI worksheet. If any of the values to be calculated are missing (A, C and D in the PASI worksheet, as well as the total PASI score), they will be calculated by Biostatistics. Summary statistics will be provided for absolute PASI scores as well as for percent change from Baseline for all study visits.

Plaque characteristic	Lesion score	Head	Upper limbs	Trunk	Lower limbs
Erythema	0 = None				
Induration/Thickness	- 1 = Slight 2 =Moderate				
Scaling	3 = Severe 4 = Very severe				
Add together the 3 score	s for each body regi	ion to give the	e Lesion Sco	re Sums (A) b	elow:
Lesion Score Sum (A)					

 Table F Psoriasis Area Severity Index Score (PASI)

Lesion Score Sum (A)					
Percent area affected	Area score (B)	Head	Upper limbs	Trunk	Lower limbs

Page 17 of 43

Degree of involvement	0 = 0%		
as a % for each body	1 = 1% - 9%		
region affected. Score	2 = 10% - 29%		
each region with value	3 = 30% - 49%		
between 0-6.	4 = 50% - 69%		
	5 = 70% - 89%		
	6 = 90% - 100%		

Multiply Lesion Score Sum (A) by Area Score (B), for each body region, to give 4 individual Subtotals (C).

Subtotals (C)				
Body Surface Area Value	0.1	0.2	0.3	0.4
Multiply each body region's Subtotal (C) by its Body Surface Area Value , i.e. x 0.1 for head, x 0.2 for upper limbs, x 0.3 for trunk, and x 0.4 for lower limbs.				
Totals (D)				
Add together the four body region scores in Totals (D) to give the final PASI Score.				

The total PASI Score will be calculated as follows:

PASI Score = D for Head + D for Upper limbs + D for Trunk + D for Lower limbs

17.2.1.7. Change in DLQI Total Score at All Study Visits

Dermatology QOL is assessed using the Dermatology Life Quality Index (DLQI, see protocol Appendix 12). Subjects will complete the DQLI questionnaire, consisting of 10 questions, at all visits.

Each question will be scored as follows:

Item	Score
Very much	3

Item	Score
A lot	2
A little	1
Not at all / Not relevant	0

- Additional scoring notes:
- A "No" at the first part of question 7 will be scored as a 0 or if "Yes' scored a 3.
- If the second part of question 7 was not answered due to answering "Not relevant" or "Yes" at the first part, it will be scored as a 0.
- The DLQI total score can range from 0 to 30 and will be derived as follows:

DLQI total score = Sum of scores for Q1 to Q10

The higher the total score, the more impaired dermatology QOL is. The change in score between visits will indicate the effect of ANB019 on the subject's dermatology QoL. Summary statistics will be provided for total and average DLQI scores as well as for percent change from Baseline for all study visits.

17.2.2. MISSING DATA METHODS FOR SECONDARY EFFICACY VARIABLE

If GPPPGA score is missing for a subject, for any reason, the score will not be imputed. Missing values for DLQI will be replaced using Last Observation Carried Forward (LOCF) for summarization of the results. All other missing values for secondary efficacy assessments will remain missing and not be imputed for any summary calculations.

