### **6.5.1 Rescue Medicine**

Rescue medication will be directed by the Investigator as needed. Rescue medication in the form of topical corticosteroids (eg, betamethasone valerate ointment and cream, mometasone furoate ointment and cream) can be used during the study for a period of up to 1 week on a daily basis on affected areas to provide symptomatic relief. The introduction of any rescue medication must be communicated and discussed with the Medical Monitor. Rescue medication will be provided by the site and reimbursed by the Sponsor.

The use of rescue medications should be delayed, if possible, for at least 1 month following the administration of study treatment. Rescue medication may be used at the Investigator's discretion only if medically indicated for the wellbeing of the subject. The date and time of rescue medication administration as well as the name and dosage regimen of the rescue medication must be recorded.

The addition of any systemic psoriasis medication that is likely to impact psoriasis signs and symptoms (eg, cyclosporine, methotrexate, and retinoid) will require the subject to be withdrawn from the study.

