### **8.1.5 Dermatology Life Quality Index**

The DLQI Questionnaire will be used to assess treatment response on the subject’s QoL. The aim of this questionnaire is to measure how much the skin condition has affected subject’s life during the previous week.

Subjects will be asked to recall their experiences during the previous week by responding to 10 questions. The DLQI will be completed by the subject on a worksheet prior to any safety or efficacy evaluations. The questionnaire is self-explanatory and handed to the subject who is asked to fill it in without the need for a detailed explanation (see [Appendix 12](#)).

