5.2. SAMPLE SIZE

The sample size is not based on statistical power considerations. Approximately 10 subjects will be enrolled at 8 study centers for study treatment.

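### DLQI alone among the continuous secondary endpoints is filled by LOCF, so its late-visit means mix measured and carried scores and can be misstated in either direction

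*SAP*

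**What the plan says.** SAP 17.2.2 gives DLQI its own rule: "Missing values for DLQI will be replaced using Last Observation Carried Forward (LOCF) for summarization of the results". For GPPPGA it says "If GPPPGA score is missing for a subject, for any reason, the score will not be imputed", and for the rest "All other missing values for secondary efficacy assessments will remain missing and not be imputed for any summary calculations". No reason is given for treating DLQI differently. The GPPPGA 0/1 proportion is a separate case: SAP 17.2.1.4 says it "will be derived using all subjects randomized and enrolled as the denominator for this calculation", so a missing score counts as not achieved.

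Exit depends on outcome. Protocol 4.1 and SAP 5.1 terminate Week 4 non-responders. Under Protocol 6.5.1, adding a systemic psoriasis drug likely to affect signs and symptoms "will require the subject to be withdrawn from the study". Protocol 7.1 makes stopping treatment equivalent to leaving the study.

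DLQI asks about the previous week (Protocol 8.1.5). It is scheduled in the combined Week 24/EOS/early-termination (ET) column of the Schedule of Activities. Protocol 7.2 makes the ET visit mandatory for early withdrawals, while Schedule footnote b only encourages it. SAP 8.4, Table B, places ET in the Week 24 slot, and SAP 8.3 bases by-visit summaries on the nominal visit while letting unscheduled values feed LOCF.

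Protocol 9.4.9 leaves missing data and possible sensitivity analysis to the SAP. SAP 17.1.4, under the primary variable, says "There will be no sensitivity analysis for this exploratory study", and the SAP text describes none for DLQI.

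**The concern.** The secondary objective is the effect on quality of life, summarised at every visit. LOCF reports a subject's last score as if it had been measured again later, although the questionnaire covers one week only. The last dose is on Day 85 and follow-up runs to Day 169, so an on-treatment score can be placed at off-treatment visits. A Week 4 non-responder's Day 29 score can fill up to seven later visits (Days 43, 57, 71, 85, 113, 141, 169), the last one 169 − 29 = 140 days on.

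Carried values enter n, mean, SD and percent change as if measured. A reader setting mean DLQI change beside mean mJDA or GPPPGA change at Week 16 or 20 would be comparing different groups without being told. With so few subjects, one carried score is visible in the mean.

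**Working it through.** **Inputs from the documents.** "Approximately 10 subjects will be enrolled at 8 study centers for study treatment" (SAP 5.2), so N = 10. DLQI runs from 0 to 30, higher being worse (SAP 17.2.1.7); 10 items × 3 = 30 agrees. The documents give no DLQI mean, SD, target effect or dropout rate, so there is no planned figure to reproduce.

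**Assumptions (not in the documents).** a = Week 4 non-responders, with change 0 at Day 29 and afterwards. b = late leavers who lose response, with last score on study −10 and true change 0 after the loss. Completers average C = −10, −7 or −5. No DLQI is taken after the loss of response.

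**Formulas.**
- Full data (everyone followed): C(10 − a − b)/10
- Observed-case: C, on n = 10 − a − b
- LOCF: [C(10 − a − b) + 0·a − 10b]/10, on n = 10
- Error of LOCF: −10b/10 = −b points
- Error of observed-case: C − C(10 − a − b)/10 = C(a + b)/10

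| C | a | b | Full data | Observed-case (n) | LOCF | LOCF error | Observed-case error |
|---|---|---|---|---|---|---|---|
| −10 | 0 | 1 | −9.0 | −10.0 (9) | −10.0 | −1.0 | −1.0 |
| −10 | 2 | 1 | −7.0 | −10.0 (7) | −8.0 | −1.0 | −3.0 |
| −7 | 0 | 1 | −6.3 | −7.0 (9) | −7.3 | −1.0 | −0.7 |
| −7 | 2 | 1 | −4.9 | −7.0 (7) | −5.9 | −1.0 | −2.1 |
| −5 | 0 | 1 | −4.5 | −5.0 (9) | −5.5 | −1.0 | −0.5 |
| −5 | 1 | 2 | −3.5 | −5.0 (7) | −5.5 | −2.0 | −1.5 |

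1. Each late leaver without a later DLQI moves the LOCF mean by 1.0 point. If the carried improvement is 5 to 15 points, this becomes 0.5 to 1.5.
2. With a = 0 and C = −10, one, two or three such leavers give a full-data mean of −9, −8 or −7 against a reported −10, an overstatement of 10/9 − 1 = 11%, 10/8 − 1 = 25% or 10/7 − 1 = 43%. Observed-case also reports −10, so its error is identical.
3. Observed-case is further off than LOCF whenever |C|(a + b) > 10b. At C = −10 this holds as soon as there is one Week 4 non-responder.
4. If non-responders improve on other care after leaving, their carried scores understate later improvement, and the LOCF error runs against the drug.

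**The ET visit.** If a DLQI at ET records the loss of response and is the value carried, LOCF equals the full-data mean and the error is 0. The order of carrying matters. Take a subject who leaves between Day 85 and Day 113. Carried by actual date, the ET score fills Weeks 16, 20 and 24. Placed only in the Week 24 slot, it leaves the favourable Day 85 score standing at Weeks 16 and 20. The SAP does not say which applies. If ET assessments are placed in the Week 24 slot, they also close the gap in n there for leavers who attend, so the table above describes Weeks 16 and 20, and Week 24 for leavers without an ET score.

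**Zero-change table.** With a = 2, b = 1 and C = −10, setting change to 0 after exit gives (7 × −10 + 3 × 0)/10 = −7.0. This equals the full-data mean by construction, because the same assumption is used. It is a bound to set beside the others, not proof of the true value.

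**The case against.** The tempting stronger reading is that LOCF overstates the quality-of-life effect and that observed-case should replace it. The documents do not support that. The only exit tied to a fixed visit is Week 4 non-response. LOCF keeps those subjects' scores in the later means, and observed-case drops them and averages the remaining responders. Keeping them also fits SAP 17.1.2, which holds Week 4 non-responders as non-responders at Week 16. The ET DLQI may record a relapse. It is also not true that every other secondary endpoint is observed-case, since the GPPPGA 0/1 proportion is not. All of this stands.

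Two further points stand in part. By-subject listings (Protocol 9.4) let a reader trace about 10 subjects individually, but they do not mark a table mean as partly carried. The table templates named in SAP 10 are not in the available text, so an observed-case DLQI table cannot be ruled out; the SAP text describes none.

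A sensitivity rule based on relapse would be undefined, because the protocol neither defines relapse nor lists it as a withdrawal reason. The rule should therefore rest on the two stated exits: Week 4 non-response and starting systemic psoriasis medication.

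**Conclusion.** The inconsistency is real and its consequence is modest. DLQI follows a different missing-data rule from the other continuous secondary endpoints, without a stated reason and where exit is related to outcome. Late-visit DLQI means can therefore mix measured and carried scores on a different n: 10 against 7 with two Week 4 non-responders and one late leaver, none with an ET score in the visit concerned.

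The size is about 1 point in the mean per late leaver of 10 with no DLQI after losing response, assuming a carried change of −10 and a return to baseline. It is 0 if an ET DLQI captures the loss and is used. The net direction depends on the mix of early and late leavers and on what happens to them after exit, which the documents do not give. A one-way overstatement is not established.

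Severity is low. The endpoint is descriptive and secondary, the study is single-arm with no hypothesis test, and the primary result is unaffected.

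**What to change.** Do not simply swap LOCF for observed-case. In SAP 17.2.1.7 and 17.2.2:

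- Present LOCF and observed-case DLQI side by side, with the number of observed and carried values at each visit.
- Add one sensitivity table in which change from baseline is set to 0 at visits after exit for subjects terminated for Week 4 non-response or withdrawn for starting systemic psoriasis medication.
- State that an ET DLQI enters LOCF by its actual date rather than only in the Week 24 slot.

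Separately, reconcile Protocol 7.2 with Schedule footnote b on whether the ET visit is mandatory or encouraged, since the carried value depends on whether that visit takes place.

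The cost is SAP wording, one or two small tables, and a smaller displayed n in the observed-case columns at late visits. No extra data collection is needed.
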